#### 4. PATIENT SELECTION

This trial will be conducted in compliance with the protocol, GCP and applicable regulations. Eligibility status must be confirmed by an Investigator or designate prior to enrollment. It is important that no exception is to be made to the eligibility criteria. Questions related to eligibility requirements must be discussed with Ozmosis and/or QI **prior** to enrollment.

##### 4.1. Inclusion Criteria

1. For inclusion in this study, patients must fulfill all the following criteria: 18 years of age or older at the time of enrollment.
2. Has previously been diagnosed with moderate to severe cGvHD OR mild cGvHD with high-risk features (defined as platelet counts  $< 100 \times 10^9/L$  at screening).
3. Capable of providing informed consent.
4. Meets the criteria of steroid-refractory cGvHD after first line therapy at the time of enrollment, as follows:
  - Lack of response or disease progression after prednisone  $\geq 1$  mg/kg/day for  $\geq 1$  week **OR**
  - Disease persistence without improvement with prednisone  $> 0.5$  mg/kg/day or 1 mg/kg/every other day for  $\geq 4$  weeks **OR**
  - Increase in prednisone dose to  $> 0.25$  mg/kg/day after 2 unsuccessful attempts to taper the dose.
5. Taking a steroid dose at the time of enrollment that is  $\leq 0.5$  mg/kg/day of prednisone or equivalent

6. Absolute neutrophil count  $\geq 1.5 \times 10^9/\text{L}$  within 2 weeks (14 days) of enrollment.
7. Platelet count  $\geq 50 \times 10^9/\text{L}$  within 2 weeks of enrollment.
8. ALT and AST  $\leq 5 \times \text{ULN}$  ( $<7.5 \times \text{ULN}$  if due to liver GvHD) within 2 weeks of enrollment.
9. Total bilirubin  $\leq 1.5 \times \text{ULN}$  within 2 weeks of enrollment.
10. Glomerular filtration rate (GFR)  $\geq 30 \text{ mL/min/1.73 m}^2$  using the MDRD-4 variable formula within 2 weeks of enrollment.
11. Female patients of childbearing potential will use 2 reliable methods of birth control (refer to Section 9.3) or be surgically sterile, or abstain from heterosexual activity for the course of the study from the time of study enrollment until 3 months following the discontinuation of all study treatment and agree not to donate or cryopreserve eggs (ova, oocytes) for the purpose of reproduction during this period. Patients of childbearing potential are those who have not been surgically sterilized (i.e. have a documented hysterectomy, or documented bilateral salpingectomy, or documented bilateral oophorectomy) or have not been free from menses for  $> 2$  years. For individuals with permanent infertility due to an alternate medical cause other than the above (e.g. Mullerian agenesis, androgen insensitivity, gonadal dysgenesis) investigator discretion should be applied to determining study entry eligibility.  
  
Male patients will use an adequate method of contraception for the course of the study from the time of enrollment to 3 months after discontinuation of all study treatment. These participants must refrain from donating or cryopreserving sperm, be abstinent from heterosexual intercourse as their preferred and usual lifestyle (abstinent on a long term and persistent basis) and agree to remain abstinent or must agree to use contraception (a male condom and an additional highly effective contraceptive method as described in Section 9.3) when having sexual intercourse with a woman of childbearing potential who is not currently pregnant.
12. The patients showing overlap syndrome with components of aGvHD at the time of enrollment can be enrolled unless their acute component of overlap syndrome is Grade 3 or 4 acute GvHD.
13. Must be able and willing to comply with study procedures.

## 4.2 Exclusion Criteria

1. Have never been treated with systemic steroids as therapy for cGvHD.

2. Receiving >0.5 mg/kg/day of prednisone or equivalent corticosteroids at the time of enrollment.
3. Ongoing use of any of the following pharmaceutical agents, which cannot be discontinued prior to belumosudil treatment (PRN/as-needed use is permissible if it can be fully discontinued at least 7 days prior to enrollment and is not expected to resume during the study):
  - Strong CYP3A inducers
  - UGT1A1 substrates (e.g., raltegravir)
  - P-gp substrates (e.g., dabigatran)
  - OATP1B1/OATP1B3/BCRP substrates (e.g., rosuvastatin)
4. Has had prior treatment with a JAK inhibitor or ROCK2 inhibitor within 8 weeks of enrollment. Participants who received a JAK inhibitor for aGvHD are eligible only if they achieved CR or PR prior to screening.
5. Active uncontrolled bacterial, fungal, parasitic, or viral infection. Infections are considered controlled if appropriate therapy has been initiated and, at the time of screening, no signs of infection are present.
6. Active hepatitis B virus (HBV) or hepatitis C virus (HCV) infection that requires treatment, or is at risk for HBV reactivation (i.e., positive HBsAg) within 4 weeks of enrollment. Participants with negative HBsAg and positive total HBc antibody may be included if HBV DNA is undetectable at the time of screening. Participants who are positive for HCV antibody are eligible only if PCR is negative for HCV RNA. Participants whose immune status is unknown or uncertain must have results confirming immune status before enrollment.
7. Known active infection or history of human immunodeficiency virus (HIV).
8. Evidence of relapsed primary hematologic disease, or receipt of treatment for relapse after the allo-HCT was performed. Patients treated with Donor Lymphocyte Infusion (DLI) who have developed GvHD will not be excluded if the primary hematological disease has resolved.
9. Maintenance therapy for the primary hematologic disease started within 4 weeks before initiation of study treatment (Cycle 1 Day 1) or plans to start maintenance therapy after Day 1.
10. Participants on mechanical ventilation, requiring oxygen support or with a FEV1 < 30%.
11. History or current diagnosis of cardiac disease indicating significant risk of safety for participation in the study, such as uncontrolled or significant cardiac disease, including any of the following:

- a. Recent myocardial infarction (within 6 months of enrollment).
  - b. New York Heart Association Class III or IV congestive heart failure.
  - c. Unstable angina (within 6 months of enrollment).
  - d. Clinically significant (symptomatic) cardiac arrhythmias (e.g. sustained ventricular tachycardia, and clinically significant second or third degree AV block without a pacemaker).
12. Uncontrolled hypertension, defined as blood pressure that remains above 130/80 mmHg in spite of concurrent use of at least three antihypertensive agents of different classes.
13. Patients with known active CNS disease (malignant involvement of CNS).
14. Patients with active acute GvHD grade III-IV.
15. History or other evidence of severe illness or any other conditions that would make the patient, in the opinion of the treating Investigator, unsuitable for the study (such as malabsorption syndromes, poorly controlled psychiatric disease or coronary artery disease).
16. Known hypersensitivity to belumosudil, ruxolitinib or any of their excipients.
17. Patients unable to swallow oral medications.
18. Female participants who are pregnant or breastfeeding.

#### **4.3 Patient Screening and Enrollment**

The screening period will commence once the informed consent form (ICF) is signed. Adequate time must be allowed for the patient to ask questions and make a voluntary decision. The ICF must be signed before any study-specific samples are taken or study-specific assessments are conducted. Data regarding screen-failures will be captured in the electronic data capture (EDC) system. In these cases, a new consent form must be signed to allow re-screening. Re-screening is permitted to occur for those who may have initially screen failed due to slightly elevated liver enzymes that, in the opinion of the treating investigator, were the result of GvHD. Re-screening for these patients can occur at any time. Re-screened participants will not be granted a new study identification number.

Prior to screening any patients, each site must have submitted all necessary regulatory documentation to Ozmosis and the site must have been activated by Ozmosis. Access to the electronic case report forms (eCRFs) will only be granted once this has been received.

All patients will be screened and confirmed to be eligible by a Qualified Investigator (QI), and consenting will occur according to the site's ethics board approved process, **prior** to the patient's enrollment into this study.

All eligibility criteria must be met at the time of enrollment. Any questions should be addressed with Ozmosis **prior** to enrollment.

No patient can receive protocol treatment until eligibility has been confirmed and the Patient Enrollment Form has been submitted to Ozmosis. The screening period is 14 days. The Patient Enrollment Form must be completed, and signed by a Site Investigator prior to enrollment. There are 2 sections to the Patient Enrollment Form:

- **SCREENING** (top section): This section is completed by the site and should be e-mailed to [[contact]](mailto:[contact]) or faxed to [contact] at the time of screening.
- **ENROLLMENT** (bottom section): This section is completed by the site at the time of enrollment. The site will submit the signed and completed Patient Enrollment Form to Ozmosis by e-mailing to [[contact]](mailto:[contact]) or fax to [contact]. Only after this has been submitted to Ozmosis can the patient receive investigational product(s)/treatment.

The protocol treatment is to be given within 3 working days of patient enrollment.

## 5. STUDY TREATMENT

### 5.1 Study Drug Administration

The Investigational Medicinal Product (IMP), Belmosudil, will be provided by Sanofi as 200 mg tablets.

Ruxolitinib will be dispensed as either 5 or 10 mg tablets, and will be obtained through the site's local pharmacy, as it will be administered per SOC.

All patients will receive open-label IMP. Responsibility for treatment of patients rests with the QI. Prior to initiating ruxolitinib (Cycle 1 Day 1), a tuberculosis skin test or interferon-gamma release assay should be performed in accordance with the approved JAKAVI® (ruxolitinib) product monograph to screen for latent tuberculosis infection, with results interpreted cautiously in immunocompromised patients. Positive results should prompt appropriate evaluation and management per institutional guidelines before starting isoniazid therapy. If the patient had been already treated with isoniazid prophylaxis for 6 months due to prior history of tuberculosis skin test or interferon-gamma release assay, this test will be exempted.

Eligible participants in this study will be started on ruxolitinib monotherapy orally at the standard recommended dose of 10 mg BID for 4 weeks (28 days). After one full cycle of ruxolitinib treatment (i.e., C2D1), the participant will have an AE assessment and, unless Grade  $\geq 3$  AE is observed, will continue on the same dose of ruxolitinib **plus** oral belumosudil 200 mg QD (or BID if receiving concomitant PPI) starting on C2D1.

In the event that the participant is experiencing Grade  $\geq 3$  AE(s) at the intended C2D1 visit assessment, treatment with belumosudil should not begin. This visit will be considered an unscheduled visit and the C2

D1 visit should be rescheduled. The participant can continue on ruxolitinib alone and should be followed for resolution of the Grade  $\geq 3$  AE(s). If the Grade  $\geq 3$  AE(s) improves to Grade  $\leq 2$  or resolves completely within 4 weeks, the participant will still be eligible to receive belumosudil. In this case, they should come back in for a true C2D1 visit and can complete all the necessary assessments as well as belumosudil dosing. If the Grade  $\geq 3$  AE(s) does not recover within 4 weeks, the participant will complete the End of Treatment visit and discontinue study. If there are any questions or concerns about the patient status and treatment in these scenarios, this should be discussed with the sponsor.

Participants will be given a study drug diary to record the details of each dose of ruxolitinib and belumosudil.

Ruxolitinib should be taken as per standard of care. Participants should take belumosudil orally with their morning or evening meal or within 5 minutes of completing the meal, taken at the same time each day. Tablets should be swallowed whole and not crushed, chewed or cut. Given there are no significant known drug interactions between ruxolitinib and belumosudil, they can be taken at the same time during combination therapy. The QI should instruct the patient to take the investigational product exactly as prescribed to promote compliance. Participants should make every effort to take the study drugs at the same scheduled time daily as described above.

## 5.2 Missed or Lost Doses

Vomited doses should not be repeated or made up. In the event that the patient misses or forgets the planned dose of study drug, the following guidance should be followed:

### Missed Belumosudil with QD Scheduling

- If less than 12 hours of time have elapsed after the missed scheduled dose, the drug should be taken. The patient should then resume the regular planned daily dosing schedule the following day.
- If more than 12 hours of time have elapsed after the missed scheduled dose, the drug should be skipped for that day. The patient should then resume the regular planned dosing schedule the following day.

### Missed Belumosudil with BID Scheduling

- For patients taking belumosudil on a BID dosing schedule, if a morning or evening dose is delayed for less than 6 hours of time, the dose should be

taken as soon as possible. The patient should then take the next dose as planned, resuming the regular dosing schedule.

- If a morning or evening dose is delayed for more than 6 hours of time, the patient should skip this dose and resume dosing with the next dose as per the original schedule in order to prevent overdosing.

Note that if the patient skips more than 7 consecutive days of both belumosudil and ruxolitinib, the patient should be discontinued from the study unless approved by the sponsor and treating Investigator.

**Doses held due to toxicity or missed will not be made up at a later time.**

### 5.3 Dose Modifications

#### **Ruxolitinib**

Dose reductions or interruptions for worsening cytopenias attributed to ruxolitinib are permitted in order to allow the patient to continue on the study treatment and should follow standard of care. For any patient who develops severe or worsening cytopenias necessitating abrupt interruption of ruxolitinib, a flare of cGvHD is expected to occur. To avoid a significant cGvHD flare during abrupt ruxolitinib interruption, the patient's corticosteroid dose should be maintained or increased to > 0.4 mg/kg/day methylprednisolone (or equivalent prednisone to > 0.5 mg/kg/day) for a minimum 7 days after abrupt cessation of ruxolitinib. Ruxolitinib dosing may be restarted or increased following recovery of the hematologic parameter(s) to what are considered acceptable levels per standard of care. The objective for restarting or escalating after a reduction for hematologic safety is to find the highest safe dosing regimen of ruxolitinib for each patient that is necessary to obtain a clinical response, with increases in dose not more than in increments of 5 mg BID and not more often than every 2 weeks.

If the reduced dose is tolerated for 4 weeks, the dose may be re-escalated to the previous dose.

#### **Belumosudil**

Table 1 and 2 below outlines the instances where belumosudil dose reductions are recommended as well as the corresponding recommended dose reduction.

**Table 1.** Guideline for management of treatment-emergent toxicities

Toxicity	Recommended Action
Grade $\geq 3$ LFTs (AST, ALT or total bilirubin)	

• Hold Belumosudil dosing until resolution to Grade 1 or below levels

• Consider resuming Belumosudil after resolution to Grade 1 or below levels. If resuming, then resume at one dose decrement

	
 
If toxicity (Grade <math>\geq 3</math>) recurs, discontinue Belumosudil
 

Other Grade $\geq 3$ clinically significant toxicities considered related to Belumosudil	
 
Hold Belumosudil dosing until toxicity has resolved to Grade 1 or below levels. If resuming Belumosudil after resolution to Grade 1 or below levels, then resume at one dose decrement
 
If toxicity recurs, hold dose as above then consider resuming Belumosudil at one dose decrement
 

Dose interruption for up to 14 days for toxicity management is permitted. Patients requiring pauses of more than 14 days will be discontinued from the study unless approved by the Sponsor.

**Table 2.** Belumosudil Dose Decrements

Belumosudil Dose	Dose Reduction
200mg BID	200mg QD
200mg QD	200mg QOD

If the reduced dose is tolerated for 1 complete cycle, the dose may be re-escalated to the previous dose.

In practice, when overlapping toxicities occur (most commonly cytopenias, liver function test abnormalities, or infections), the treating physician will exercise clinical judgment to prioritize dose modification based on the dominant contributing agent, severity of the toxicity, and organ-specific involvement. As a general guiding principle:

- For hematologic toxicities (e.g., thrombocytopenia, neutropenia): ruxolitinib will be dose-reduced or interrupted first, as it is the primary agent associated with JAK2-mediated cytopenias, per the product monograph.
- For liver function test elevations (e.g., bilirubin, ALT/AST): belumosudil will be dose-reduced or interrupted first, consistent with its dose modification tables (Table 1 and Table 2), unless the QI determines ruxolitinib is the more likely contributor based on timing and clinical context.

**Table 3.** Dose modification for clinically relevant hematologic side effects

Toxicity	Ruxolitinib	Belumosudil
Neutropenia (ANC)		
Grade 1-2 (ANC LLN- $1 \times 10^9/L$ )	Maintain the dose	Maintain the dose
Grade 3 (ANC $0.5-1 \times 10^9/L$ )	Reduce the dose to half, If resolve to Grade 2 or lower in 7 days, escalate to the initial dose	Maintain the dose If not resolve to Grade 2 or lower in 7 days, hold Belumosudil until recover.

	If not resolve in 7 days, hold Ruxolitinib until recover. When recover, restart it at one dose decrement.	When recover, restart it at initial dose
Grade 4 (ANC $<0.5 \times 10^9/L$ )	Hold the dose If resolve to Grade 2 or lower in 7 days, restart at the half of initial dose If not resolve in 7 days, hold Ruxolitinib until recover. When recover, restart it at one dose decrement.	Hold the dose If resolve to Grade 2 or lower in 7 days, restart at the half of initial dose If not resolve in 7 days, hold Ruxolitinib until recover. When recover, restart it at one dose decrement.
Thrombocytopenia (transfusion allowed if needed)		
Grade 1-2 (Platelet LLN- $50 \times 10^9/L$ )	Maintain the dose	Maintain the dose
Grade 3 (ANC 25- $50 \times 10^9/L$ )	Reduce the dose to half, If resolve to Grade 2 or lower in 7 days, escalate to the initial dose If not resolve in 7 days, hold Ruxolitinib until recover. When recover, restart it at one dose decrement.	Maintain the dose If not resolve to Grade 2 or lower in 7 days, hold Belumosudil until recover. When recover, restart it at initial dose
Grade 4 (ANC $<25 \times 10^9/L$ )	Hold the dose If resolve to Grade 2 or lower in 7 days, restart at the half of initial dose If not resolve in 7 days, hold Ruxolitinib until recover. When recover, restart it at one dose decrement.	Hold the dose If resolve to Grade 2 or lower in 7 days, restart at the half of initial dose If not resolve in 7 days, hold Ruxolitinib until recover. When recover, restart it at one dose decrement.

**Table 4.** Dose modification for clinically relevant non-hematologic side effects

Toxicity	Ruxolitinib	Belumosudil
LFTs (AST, ALT or total bilirubin)		
Grade 1-2	Maintain the dose	Maintain the dose
Grade 3-4	Maintain the dose If not resolve to Grade 2 or lower in 7 days, hold Ruxolitinib until recover.	Hold Belumosudil dosing until resolution to Grade 2 or below levels Consider resuming Belumosudil after

	When recover, restart it at initial dose	resolution to Grade 2 or below levels. If resuming, then resume at one dose decrement If toxicity (Grade $\geq 3$ ) recurs, discontinue Belumosudil
Other Grade <math>\geq 3</math> clinically significant toxicities considered related to Belumosudil		
Grade 1-2	Maintain the dose	Maintain the dose
Grade 3 (ANC 25-50x10  /L)	Maintain the dose If not resolve to Grade 2 or lower in 7 days, hold Ruxolitinib until recover. When recover, restart it at initial dose	Hold Belumosudil dosing until toxicity has resolved to Grade 2 or below levels. If resuming Belumosudil after resolution to Grade 2 or below levels, then resume at one dose decrement If toxicity recurs, hold dose as above then consider resuming Belumosudil at one dose decrement

**Table 5.** Recommendation for Dose Decrease of both Belumosudil and Ruxolitinib

Previous dose	Recommended dose for dose decrease
Belumosudil	
200mg BID	200mg QD
200mg QD	200mg QOD
200mg QOD	discontinue
Ruxolitinib	
10mg BID	5mg BID (or 10mg QD)
5mg BID	5mg QD
5mg QD	discontinue

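### Section 5.3 gives two recovery grades for restarting belumosudil after the same toxicity: Grade 1 or below in Table 1, Grade 2 or below in Table 4

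*Protocol*

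**What the plan says.** Protocol Section 5.3 (Dose Modifications) covers non-hematologic toxicity on belumosudil in two tables.

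**Table 1**, under the Belumosudil subheading, has two rows. For AST, ALT or total bilirubin at Grade 3 or higher it says "Hold Belumosudil dosing until resolution to Grade 1 or below levels", and then "Consider resuming Belumosudil after resolution to Grade 1 or below levels. If resuming, then resume at one dose decrement". For other clinically significant belumosudil-related toxicity at Grade 3 or higher it says "Hold Belumosudil dosing until toxicity has resolved to Grade 1 or below levels", and repeats Grade 1 as the grade for resuming at one decrement.

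**Table 4**, whose title covers non-hematologic side effects in general, has a belumosudil column for the same two categories. For the same liver tests at Grade 3-4 it says "Hold Belumosudil dosing until resolution to Grade 2 or below levels", and allows resumption to be considered after "resolution to Grade 2 or below levels. If resuming, then resume at one dose decrement". For other toxicity, under a block heading matching Table 1's row label, it says "Hold Belumosudil dosing until toxicity has resolved to Grade 2 or below levels", followed by "If resuming Belumosudil after resolution to Grade 2 or below levels, then resume at one dose decrement".

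Between the two tables, Section 5.3 permits interruptions of up to 14 days for toxicity and adds: "Patients requiring pauses of more than 14 days will be discontinued from the study unless approved by the Sponsor".

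**The concern.** These are two current instructions for the same drug and the same event, and they differ in the earliest restart they allow. A site that opens Table 1 and a site that opens Table 4 can treat the same patient differently while each follows the protocol.

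Two things are at stake. The first is re-exposure: Section 10.5 lists ALT, AST and bilirubin of Grade 3 or higher as adverse events of special interest, so the restart rule after such an event is a safety instruction. Section 10.5 itself sets no restart grade. The second is retention: with a 14-day limit on interruptions, a stricter recovery grade gives a slowly recovering patient less chance of restarting in time. A patient still at Grade 2 as day 14 approaches could restart under one table and would need Sponsor approval to remain on study under the other.

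**Working it through.** No arithmetic beyond a count is needed. The check sets the two tables side by side and then looks for text that ranks them.

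**Step 1. Compare the instructions.**

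| Toxicity | Instruction | Table 1 | Table 4, belumosudil column |
|---|---|---|---|
| AST, ALT, bilirubin | Hold until | Grade 1 or below | Grade 2 or below |
| AST, ALT, bilirubin | Resume after | Grade 1 or below | Grade 2 or below |
| Other related, Grade 3 or higher | Hold until | Grade 1 or below | Grade 2 or below |
| Other related, Grade 3 or higher | Resume after | Grade 1 or below | Grade 2 or below |

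Table 1 states its threshold 2 + 2 = 4 times and Table 4 states its threshold 2 + 2 = 4 times. Each table agrees with itself, so this is not a single slip that a reader could correct. Both toxicity rows of Table 1 (2 of 2) are contradicted, by one CTCAE grade.

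**Step 2. See what else differs.** Both tables restart at one dose decrement. Both discontinue belumosudil if Grade 3 or higher liver toxicity recurs, and both give the same recurrence instruction for other toxicity. For these belumosudil instructions, the recovery grade is the substantive difference.

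**Step 3. Look for a rule of precedence or separate scope.**

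- The liver-test bullet between the tables refers to Tables 1 and 2 as belumosudil's dose modification tables. It settles which of the two drugs is reduced or interrupted first. It sets no recovery grade, does not mention Table 4 and does not reach the other-toxicity row.
- Table 4 follows the paragraph on overlapping toxicities, but its title is general. Belumosudil is added to ruxolitinib from C2D1, so patients on belumosudil are ordinarily on both drugs. Position in the section does not give the tables separate populations.
- Section 5.1 accepts recovery to Grade 2 or below before the first belumosudil dose when a Grade 3 or higher event is present at the planned C2D1 visit. That is a first dose, not a restart after toxicity on belumosudil.

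None of these resolves the conflict.

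**Step 4. Follow one patient.** A liver test rises to Grade 3 and belumosudil is held. It falls to Grade 2 and stays there. Table 1 advises continuing the hold; Table 4 allows a restart at one decrement. If the hold passes 14 days, the patient leaves the study unless the Sponsor approves otherwise.

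**Step 5. Check neighbouring cells for errors to correct at the same time.**

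- Table 3: both Grade 4 cells in the belumosudil column (neutropenia and thrombocytopenia) tell the site to hold ruxolitinib if there is no recovery in 7 days. This looks copied from the ruxolitinib column.
- Table 3: the Grade 3 and Grade 4 thrombocytopenia rows are labelled ANC where platelets are meant.
- Table 4: the action row for other toxicity carries an ANC range that does not belong there. The row label says Grade 3, while the block heading says Grade 3 or higher.

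**The case against.** The best defence is that Table 1 is guidance. Its title calls it a guideline, its column lists recommended actions, and Section 5.3 leaves overlapping toxicities, including liver test abnormalities, to clinical judgment. Resumption is optional in both tables, so an investigator who waits for Grade 1 complies with both, and some variation between sites would remain even with a single threshold. Sponsor approval is available for pauses beyond 14 days. The liver-test bullet also gives a site some reason to treat Table 1 as the leading rule for liver tests.

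Most of this stands as mitigation. It rules out saying that Table 1 obliges the site to keep a Grade 2 patient on hold; the text supports only that it advises this. It does not remove the conflict. Discretion works above a stated minimum, and here there are two minimums. The hint in the liver-test bullet concerns the order of drug modification and is silent on the other-toxicity category.

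Three stronger readings might be inferred and are not supported:

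- That the other-toxicity conflict is confined to Grade 3. This rests on a row label that already contains a stray ANC range, under a heading that says Grade 3 or higher. The row's intended scope cannot be settled from the text.
- That a Grade 1 threshold clashes with inclusion criterion 8, which admits ALT and AST up to 5 x ULN, or below 7.5 x ULN if due to liver GvHD. Testing this needs CTCAE grade cut-offs, which the protocol does not reproduce.
- That the primary efficacy result is materially distorted. The protocol gives no incidence of these events and no recovery times, so no such effect can be sized.

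**Conclusion.** The inconsistency is real and should be corrected. Section 5.3 gives two recovery thresholds, one grade apart, for resuming belumosudil after the same toxicity. They cover both categories in Table 1, and no text says which governs. The practical consequence falls on patients who improve to Grade 2 but not to Grade 1: whether they may be re-exposed, and whether they pass the 14-day limit, depends on the table the site uses.

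The conclusion rests only on the current wording of Section 5.3 and on no assumed rate. It is a matter of clear safety instructions. The sample size of 63, the criterion of 37 responders and the planned analyses do not change.

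**What to change.** State one recovery threshold in both Table 1 and Table 4, for liver tests and for other related toxicity. Use Grade 1 or below, the stricter existing rule and the one that satisfies both tables, unless the clinical team documents a reason for Grade 2. Deleting the duplicate belumosudil rows from one table would serve equally well.

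In the same amendment:

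- Table 3: in the two Grade 4 belumosudil cells, name belumosudil, not ruxolitinib, as the drug to hold.
- Table 3: relabel the Grade 3 and Grade 4 thrombocytopenia rows from ANC to platelets.
- Table 4: remove the ANC range from the other-toxicity action row, and state whether that row covers Grade 3 only or Grade 3 and above.

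The cost is a protocol clarification and a notice to sites. If Grade 1 is chosen, some holds may be somewhat longer, and more patients may then need Sponsor approval to continue past 14 days.
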